4 DETERMINATION OF SAMPLE SIZE

The proposed sample size was based on comparisons of the primary efficacy variable, with the response rate defined as the proportion of subjects who do not require a platelet transfusion or any rescue procedure for bleeding after randomization and up to 7 days following an elective procedure. Based on clinical opinion and the published results of a similar compound in adults with thrombocytopenia associated with liver disease (ELtrombopag EValuated for its Ability to overcome Thrombocytopenia and Enable procedures [ELEVATE] study [Afdahl, 2012])², the response rate in the placebo group is assumed to be 18%. Within each baseline platelet count cohort, a sample size of 100 randomized subjects, 67 subjects for avatrombopag and 33 subjects for placebo, would have greater than 90% power to detect an absolute difference of 35% between the avatrombopag response rate and the placebo response rate assuming 18% response rate for placebo using Fisher's Exact tests with a 2-sided $\alpha=0.05$. The hypothesized treatment group difference was based on platelet count changes found in the Phase 2 study (E5501-G000-202) and dose-response modeling using data from that study and others in the project development. Based on the baseline data in the Phase 2 study and assuming these were projected to be similar for this study, it was anticipated that this study would enroll roughly half of the total number of subjects in each of the 2 baseline platelet count cohorts to make the total sample size of 200 randomized subjects, 133 subjects for avatrombopag and 67 subjects for placebo.

5 STATISTICAL METHODS

Descriptive statistics will be reported for continuous variables using mean, standard deviation (SD), median, minimum and maximum. Categorical variables will be summarized using frequency count as number (percentage) of subjects. Graphical displays of the data might be presented where appropriate to aid interpretation.

5.1 STUDY ENDPOINTS

5.1.1 Primary Endpoint(s)

The primary efficacy endpoint is the proportion of subjects who do not require a platelet transfusion or any rescue procedure for bleeding after randomization and up to 7 days following an elective procedure.

5.1.2 Secondary Endpoint(s)

The secondary efficacy endpoints are:

- Proportion of responders defined as subjects who achieve platelet counts of $\geq 50 \times 10^9/L$ on Procedure Day (i.e., prior to receiving a platelet transfusion or undergoing the elective procedure)
- Change from baseline in platelet count on Procedure Day (i.e., prior to receiving a platelet transfusion or undergoing the elective procedure)

5.1.3 Exploratory Endpoint(s)

The exploratory endpoints are:

- Platelet count and change from baseline in platelet count at each visit
- Proportion of responders defined as subjects who achieve platelet counts of $\geq 50 \times 10^9/L$, $\geq 75 \times 10^9/L$, or $\geq 200 \times 10^9/L$ at each visit
- Number of platelet units used per platelet transfusion episode
- Severity of bleeding event assessed by WHO bleeding score and Bleeding Academic Research Consortium (BARC) bleeding scale
- Proportion of subjects with a WHO bleeding score ≥ 2 after randomization and up to 7 days following an elective procedure
- Health economics assessed by resource use

5.2 STUDY SUBJECTS

5.2.1 Definitions of Analysis Sets

Full Analysis Set (FAS): The FAS is the group of all subjects who are randomized into the study.

Per Protocol Analysis Set (PP): The PP is the group of all randomized subjects who receive protocol-assigned study drug and do not meet any of the following criteria:

- Baseline platelet count of $>50 \times 10^9/L$
- Subjects who were enrolled in the study despite not being planned for transfusion even in the event of no significant increase of platelet count
- Taking prohibited prior medications or prior transfusion
- Presence of significant bleeding at baseline
- Did not have a protocol permitted procedure on Day 8 - 15
- Received dose different from the intended dose
- Received $<80\%$ of the total dose or received $>40\%$ of total dose without food
- No elective procedures or elective procedure outside day 8-15
- Subject received platelet transfusion before knowing V4 platelet count
- Subject refused platelet transfusion

Subjects who met any of the criteria listed above will be excluded from the PP due to possible introduction of bias.

Safety Analysis Set: The Safety Analysis Set is the group of subjects who receive at least one dose of study drug and have at least one post dose safety assessment.

The number (percentage) of subjects in each analysis set will be summarized by treatment groups using descriptive statistics. The summaries for FAS and PP will be based on subjects “as randomized”. The summary for Safety Analysis Set will be based on subjects “as treated”.

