##### 9.4.7.3 Prohibited Concomitant Therapy

Erythropoietin stimulating agents are prohibited throughout the study. Interferon use is prohibited during the study; however, at the investigator's discretion, subjects may restart IFN therapy if clinically indicated during the Follow-up Phase (ie, after Visit 4 [Procedure Day]).

Eltrombopag, romiplostim, heparin, warfarin, NSAIDs, aspirin, verapamil, estrogen, and antiplatelet therapy with ticlopidine or glycoprotein IIb/IIIa antagonists (eg, tirofiban) are prohibited. (revised per Amendment 02) Aspirin, for antiplatelet therapy, can be prescribed at the discretion of the investigator in subjects in which the platelet count rises and who are believed to have an increased risk of thrombosis. In subjects where use of aspirin is contraindicated, an alternate antiplatelet therapy such as a platelet adenosine diphosphate receptor inhibitor (eg, clopidogrel) can be prescribed. It should be noted that clopidogrel should be used with due consideration in subjects with liver disease. Lack of activation due to liver disease could lead to a reduction in activation of the prodrug. In addition, as clopidogrel is activated by the CYP system, care is required when administering clopidogrel to subjects with liver disease and co-administering clopidogrel with agents that are substrates or inhibitors of CYP.

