### 9.7.1.2 Definitions of Analysis Sets

Full Analysis Set (FAS): The FAS is the group of randomized subjects. The FAS will be analyzed “as randomized”.

Per Protocol Set (PP): The PP Set is the group of all randomized subjects who receive protocol-assigned study drug and do not meet any of the following criteria:

- Subjects who have any major protocol violations (major inclusion/exclusion violations or other major protocol violations that impact the evaluation of efficacy)
- Subjects who use a prohibited concomitant medication that affects the assessment of study endpoints
- Subjects who are noncompliant in terms of study medication

A comprehensive list of subjects to be excluded from the PP will be agreed upon by the study team prior to database lock. The PP will be analyzed “as randomized”.

Safety Analysis Set: The Safety Analysis Set is the group of subjects who receive at least 1 dose of study drug and have at least 1 postdose safety assessment. This set will be analyzed “as treated.”

PK Analysis Set: The PK Analysis Set is the group of randomized subjects who receive at least 1 dose of avatrombopag and have at least 1 quantifiable avatrombopag concentration with a documented dosing history.

PK/PD Analysis Set: The PK/PD Analysis Set is the group of randomized subjects who receive at least 1 dose of avatrombopag, have at least 1 quantifiable avatrombopag concentration, and at least 1 platelet count, with a documented dosing history.

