5.2.5 Prior and Concomitant Therapy

All investigator terms for medications recorded on the CRF will be coded using the WHO Drug Dictionary (WHO DD).

Prior medications are defined as medications that stop prior to the first dose of study drug. Concomitant medications are defined as medications that (1) start before the first dose of study drug and are continuing at the time of the first dose of study drug, or (2) start on or after the date of the first dose of study drug, up to 30 days after the last dose of study drug.

The number (percentage) of subjects who take prior and concomitant medications will be summarized using the Safety Analysis Set by treatment group, Anatomical Therapeutic Chemical (ATC) Classification, and WHO DD preferred term. In addition, the number (percentage) of subjects who take the concomitant medications associated with elective procedures will also be summarized using the Safety Analysis Set by treatment group, ATC Classification, and WHO DD preferred term.

If a subject takes the same medications for the same class level or drug name, the subject will be counted only once for that class level or drug name.

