7 CHANGES IN THE PLANNED ANALYSES

SAP version (Final 3.0) is updated based on Protocol Amendment 04 with the following changes:

- Sections 3.1.2, 3.1.3, 5.1.2, 5.1.3, 5.3.3.1, 5.4.2, 5.4.2.3, 5.4.3 and 5.4.3.5: Efficacy endpoint "Proportion of subjects with a WHO bleeding score ≥ 2 after randomization and

up to 7 days following an elective procedure” is moved from secondary to exploratory endpoint to match the protocol amendment 4. These sections have been updated to reflect this change.

- Section 4: Sample size is reduced from 300 to 200. This section has been updated to match the protocol amendment 4.
- Section 5.4.2.2: Calculation of 95% CI for change from baseline in platelet count on Procedure Day for each treatment group within each baseline platelet count cohort has been removed to ensure consistency with the study objectives.
- Section 5.7.1: This section is updated to reflect that only listings will be provided for the Health Economics Assessment.
- Section 5.2.1: Per-Protocol exclusion criteria are finalized.

SAP version (Final 2.0) was updated based on Protocol Amendment 02 with the following changes:

- Section 3.2 table 1, and sections 5.2.4, 5.3.2, 5.3.4, 5.4.1, 5.4.1.2 and 5.4.2.1: Categorization of risk of bleeding is updated to match protocol amendment 02
- Section 5.6.6.3: Listing of platelet function test assessed using platelet aggregometry has been added.
- Section 13.1: "Fasting Glucose value" has been added to the criteria for determining grade 3 and 4 in the lab grading table.

SAP version (Final 2.0) was also updated from version Final 1.0 to ensure consistency with the eCRF/protocol as follows:

- Section 5.6.5: ECG interpretation category is updated.
- Section 5.2.4: Baseline summaries of creatinine clearance and disease etiology, and subgroup analysis by disease etiology have been added.

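### The SAP's per-protocol list covers prohibited prior medication only and has no counterpart to the protocol's exclusion for prohibited concomitant medication

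*SAP*

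**What the plan says.** Protocol 9.7.1.2, repeated in the Synopsis under Analysis Sets, gives three reasons for leaving the PP set:

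- major violations: "Subjects who have any major protocol violations (major inclusion/exclusion violations or other major protocol violations that impact the evaluation of efficacy";
- on-study medication: "Subjects who use a prohibited concomitant medication that affects the assessment of study endpoints";
- noncompliance with study drug.

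It adds that the study team will agree a subject-level list of PP exclusions before database lock.

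SAP 5.2.1 puts ten specific items in place of these three. The only item on medication is "Taking prohibited prior medications or prior transfusion". The list closes with its operating rule: "Subjects who met any of the criteria listed above will be excluded from the PP due to possible introduction of bias". SAP Section 7 records the change in a single line: "Per-Protocol exclusion criteria are finalized".

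SAP 5.2.5 keeps prior and concomitant use apart. "Prior medications are defined as medications that stop prior to the first dose of study drug". Concomitant medications are those continuing at first dose, or those that "start on or after the date of the first dose of study drug, up to 30 days after the last dose of study drug".

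Protocol 9.4.7.3 prohibits during the study, among others, "Eltrombopag, romiplostim, heparin, warfarin, NSAIDs, aspirin, verapamil, estrogen". Protocol 7.1.1 identifies the first two as thrombopoietin-receptor agonists.

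**The concern.** A PP analysis is meant to show the treatment comparison in subjects who followed the protocol closely enough for their outcome to be interpretable. A subject given a second drug of the test drug's class between first dose and the end of the endpoint window is an obvious candidate for exclusion, and the protocol says so. Under the SAP list that subject meets no exclusion.

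The case is not far-fetched. The rationale recorded for Amendment 02, which added eltrombopag and romiplostim to the prohibited list, is that both are in off-label use in this setting. The anticoagulants and antiplatelet agents on the same list bear on bleeding, and so on the rescue component of the endpoint.

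At stake is whether the supportive PP analysis matches the protocol's definition, and whether two programmers, one working from each document, would build the same set.

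**Working it through.** **Line-by-line comparison**

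| Protocol 9.7.1.2 exclusion | Counterpart in SAP 5.2.1 |
|---|---|
| Major protocol violations | Partial: items on baseline count, planned transfusion, prohibited prior medication or transfusion, bleeding at baseline, procedure type and timing, transfusion before the Visit 4 count, and refused transfusion. No general item. |
| Prohibited concomitant medication affecting the endpoints | None |
| Noncompliance with study drug | Items on wrong dose, less than 80% of the dose, and more than 40% of the dose without food |

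**Can the prior-medication item be read to include on-study use?** Not under SAP 5.2.5. A drug started on or after first dose is concomitant. So is one started earlier and still being taken at first dose. Neither is prior.

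**Does other SAP text fill the gap?** SAP 5.2.3 has a deviation category for use of prohibited treatments, but its stated output is listing and summary by category and treatment group. Nothing there links it to PP membership.

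**Is the removal declared?** SAP Section 7 declares that 5.2.1 changed. It does not say that this criterion was dropped, or why.

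**The plan's own figure.** The nearest planning figure is power above 90% per cohort (SAP Section 4), with 67 avatrombopag and 33 placebo subjects, 18% placebo response, a 35-point difference (so 53% on avatrombopag) and Fisher's exact test at two-sided 0.05. Full enumeration gives 92.6%; the normal approximation gives 94.5%. The stated figure reproduces.

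**Illustrative size.** The documents give no rate of prohibited use, so the following is assumed: k of 33 placebo subjects in one cohort take another thrombopoietin-receptor agonist and respond at 53%, the other 33 − k respond at 18%, and no one else leaves the set.

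Placebo response with these subjects kept = [(33 − k) × 0.18 + k × 0.53] / 33

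- k = 1: (5.76 + 0.53)/33 = 19.06%; difference 53 − 19.06 = 33.9 points
- k = 2: (5.58 + 1.06)/33 = 20.12%; difference 32.9 points
- k = 3: (5.40 + 1.59)/33 = 21.18%; difference 31.8 points

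| k | Difference, kept | Fisher power, kept | Difference, excluded | Fisher power, excluded |
|---|---|---|---|---|
| 0 | 35.0 | 92.6% | 35.0 | 92.6% |
| 1 | 33.9 | 90.5% | 35.0 | 91.7% |
| 2 | 32.9 | 88.1% | 35.0 | 92.2% |
| 3 | 31.8 | 85.3% | 35.0 | 91.9% |

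These powers use the planning test and full cohort sizes. They describe sensitivity only: the PP analysis itself repeats the stratified CMH test, in a set that will be smaller for other reasons.

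**The case against.** The strongest reply is that such a subject would be identified and could still be removed. The protocol requires an agreed subject-level list before lock, SAP 5.2.3 has major deviations reviewed before lock and unblinding with prohibited treatment as a named category, and the SAP says it is prepared from the protocol. This stands as mitigation. It does not close the gap, because a subject-level list applies criteria, and none of the criteria the SAP calls final would remove this subject. A team that removed one would be following the protocol against the SAP.

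Second, the PP set is supportive. SAP 5.3 makes the FAS primary, SAP 5.4.1.1 lists PP as one of four sensitivity analyses, and success rests on the primary endpoint in both cohorts. This stands in full.

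Third, in the illustration the retained subjects shrink the apparent benefit, which is conservative for a superiority claim. That is true for use in the placebo arm. Use in the avatrombopag arm could enlarge the difference.

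Fourth, simply restoring the criterion could itself introduce bias. Protocol 9.4.7.3 lists aspirin as prohibited, yet lets the investigator prescribe it, or an alternate antiplatelet agent, when the platelet count rises and thrombosis risk is believed increased. Counting that use as a violation would remove subjects because their platelets rose, plausibly more often on avatrombopag. This stands, and the fix has to deal with it.

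**Conclusion.** The mismatch is real and minor. A PP set built from the SAP list as written would not apply a rule that the protocol states twice. The primary FAS test and the success rule are unaffected. On assumed use by 1 to 3 of 33 placebo subjects in a cohort, all responding at 53%, the expected PP difference moves from 35 to between 33.9 and 31.8 points. If no one took such a drug, nothing changes.

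Three stronger readings are tempting and are not supported:

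- *The PP analysis no longer shows the effect under adherence.* The ten items still remove wrong or insufficient dosing, mistimed or absent procedures, transfusion before the Visit 4 count, and key eligibility failures. One gap makes the set less clean; it does not defeat it. With no rate of prohibited use given, nothing shows that these would be the most contaminated subjects.
- *Two subjects would shift the placebo rate by 5 points.* That figure compares 6/33 = 18.2% with 4/31 = 12.9%. It requires both subjects to respond with certainty, and the planned 18% to include them already. The SAP assumes 18% without mentioning such use. On the plan's own rates, two subjects move the expected difference by about 2 points.
- *The criterion was deliberately removed without disclosure.* Section 7 does declare a change to 5.2.1. What is missing is an itemised statement. The list also states the Day 8–15 procedure condition twice, which is at least as consistent with a drafting slip.

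**What to change.** Before unblinding, reconcile SAP 5.2.1 with Protocol 9.7.1.2:

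- Add the protocol's criterion ("Subjects who use a prohibited concomitant medication that affects the assessment of study endpoints") to the SAP list, limited to use between first dose and 7 days after the procedure. The window is needed because SAP 5.2.5 counts concomitant medication to 30 days after last dose, whereas the primary endpoint stops 7 days after the procedure. Subjects without a procedure already leave PP under another item.
- Have the judgement made blind, before database lock, alongside the protocol's subject-level list.
- State that use the protocol itself permits in Section 9.4.7.3 (discretionary aspirin or alternate antiplatelet therapy after a platelet rise, and interferon restarted in follow-up) does not count as prohibited for PP. This is a classification for the analysis set only; it takes no position on the clinical rule.
- Leave the prior-transfusion wording as it is.
- Itemise the change in SAP Section 7. If the omission was intended, record the reason there instead.

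The cost is a line or two of SAP text. Concomitant medications are already collected and coded. A few subjects may leave the PP set. Planned sample size, alpha and the FAS analysis do not change.

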Study E5501-G000-202 evaluated the efficacy, safety, and population PK of once-daily oral avatrombopag dosing, in subjects with chronic liver diseases and thrombocytopenia prior to elective surgical or diagnostic procedures. The primary efficacy endpoint was the proportion of responders with platelet count increases from baseline of  $\geq 20 \times 10^9/L$  and a platelet count of  $\geq 50 \times 10^9/L$  once from Day 4 through Day 8. The proportion of responders for all avatrombopag-treated subjects was 48.4% compared with 8.1% in the combined placebo group ( $P < 0.0001$ ). All doses of avatrombopag achieved a significantly higher proportion of responders compared with their respective cohort placebo arms and the highest platelet count responses were observed between Days 10 to 14 after first dose. In addition, avatrombopag appeared well tolerated in this patient population. There was no clear trend regarding the incidences of AEs between placebo and avatrombopag treatment groups, and the commonly reported treatment-emergent adverse events (TEAEs) and serious TEAEs were consistent with the disease state of the patient population. The findings from Study E5501-G000-202 suggest that avatrombopag would be an effective therapy for the treatment of thrombocytopenia in patients with chronic liver disease, prior to an elective procedure.

For more detailed information regarding effects in humans, please refer to the Investigator Brochure.

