Portal vein thrombosis in the general population is a rare event. However, it is a relatively common complication in patients with liver cirrhosis (4% - 15%), with frequencies increasing with the degree of cirrhosis and a prevalence as high as approximately 30% in candidates for liver transplantation. Although even complete occlusion of the portal vein may not result in overt clinical manifestations, due to rapid development of collateral veins bypassing the thrombosed segment, patients can experience acute and chronic onset of a variety of clinical symptoms. These include increased variceal bleeding, refractory ascites and abdominal pain, presumably from small bowel ischemia or infarction due to the involvement of the superior mesenteric vein. Furthermore, the occurrence of PVT is known to increase the risk of mortality both prior to and post liver transplantation. Eltrombopag, a currently marketed TPO-receptor agonist for the treatment of ITP, has been reported to have been associated with the occurrence of PVT in patients with chronic liver disease and thrombocytopenia. In the ELtrombopag EValuated for its Ability to overcome Thrombocytopenia and Enable procedures (ELEVATE) study, aimed at decreasing the requirement for platelet transfusion prior to elective procedures, there was an imbalance in the incidence of PVT and mesenteric thrombosis between the active and placebo arms. In addition to very high and prolonged elevations in platelet counts (26% of eltrombopag-treated subjects reached  $>200 \times 10^9/L$  and 5% reached  $>400 \times 10^9/L$ ); 6 (4%) subjects in the eltrombopag arm and 1 (1%) in the placebo arm experienced a thrombotic event

of the portal venous system, leading to early termination of the study. In the current Phase 3 program, avatrombopag doses and treatment duration have been selected so that platelet count elevations are transient and not excessive, with the projected percentage of subjects who reach  $>200 \times 10^9/L$  limited to  $<2\%$ . During this study, if a potential PVT is suspected, subjects will undergo confirmation of diagnosis and appropriate treatment as per local guidelines.

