## 9 INVESTIGATIONAL PLAN

### 9.1 OVERALL STUDY DESIGN AND PLAN

This is a Phase 3, global, multicenter, randomized, double-blind, placebo-controlled, parallel-group study using avatrombopag to treat adults with thrombocytopenia associated with liver disease prior to an elective procedure. Subjects will be enrolled into 2 cohorts according to mean baseline platelet count and, within each baseline platelet count cohort, will be further stratified by risk of bleeding associated with the elective procedure (low, moderate or high) and hepatocellular carcinoma (HCC) status (Yes or No). Neither baseline platelet count cohort will comprise greater than 55% of the total number of subjects enrolled into the study. The estimated study duration to enroll and complete all subjects is approximately 20 months.

Within the **lower** baseline platelet count cohort ( $<40 \times 10^9/L$ ) and each stratum, subjects will be randomized by an interactive voice and web response system (IxRS) in a 2:1 ratio to receive avatrombopag or placebo as follows:

- 60 mg avatrombopag on Days 1 to 5 (Group A: avatrombopag, lower baseline platelet count)
- Matching placebo on Days 1 to 5 (Group B: placebo, lower baseline platelet count)

Within the **higher** baseline platelet count cohort (from 40 to  $<50 \times 10^9/L$ ) and each stratum, subjects will be randomized in a 2:1 ratio to receive avatrombopag or placebo as follows:

- 40 mg avatrombopag on Days 1 to 5 (Group C: avatrombopag, higher baseline platelet count)
- Matching placebo on Days 1 to 5 (Group D: placebo, higher baseline platelet count)

Platelet counts must be measured on 2 separate occasions, during the Screening Period and at Baseline, and must be performed at least 1 day apart with neither platelet count  $>60 \times 10^9/L$ . The mean of these 2 platelet counts (mean baseline platelet count  $<50 \times 10^9/L$ ) will be used for entry criteria.

The elective procedure must be scheduled to be performed within 10 to 13 days of first dose of study drug and after Visit 4 assessments have been performed.

This study will consist of 3 phases: Prerandomization, Randomization, and a Follow-up Phase.

The Prerandomization Phase consists of a Screening Period that will take place from Day -14 through Day -1.

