#### 9.1.2.3 Procedure Day (Visit 4)

This will occur 5 to 8 days after the last dose of study drug (on Study Day 10 to 13).

All Procedure Day assessments are to be completed prior to the procedure and include assessments shown in [Section 9.5.2.1 \(Table 5\)](#).

In addition, all subjects are required to return study drug and the dosing diary at this visit.

The elective procedure for those subjects whose preprocedural platelet count is  $>200 \times 10^9/L$  on Visit 4 (Procedure Day) may be delayed at the discretion of the investigator until platelet counts are below  $200 \times 10^9/L$ . All subjects whose platelet count exceeds  $200 \times 10^9/L$  will be required to have a Doppler assessment at Visit 5. For any subjects where the presence of a PVT is suspected, confirmation of diagnosis, via CT scan or MRI, should be performed and treatment for PVT initiated per local guidelines.

Permitted procedures and the risk of bleeding associated with each procedure are listed in [Table 1](#). It is planned that no fewer than 10% of subjects will be enrolled into the high risk group and no more than 60% of subjects in the low-risk group.

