#### **9.4.4 Selection of Doses in the Study**

Dose selection has been carefully focused on seeking to maintain an appropriate risk:benefit ratio balance in this patient population, removing the requirement for platelet transfusion, or any rescue procedure for bleeding, while minimizing the risk of thromboembolic events. The selected doses, based on modeling and simulation of the E5501-G000-202 study data, are aimed at achieving sufficient efficacy (eliminating the need for platelet transfusion) while specifically limiting the proportion of subjects achieving platelet counts  $>200 \times 10^9/L$  to less than 2%.

The current study design employs a dosing regimen according to baseline platelet count that is anticipated to lead to a similar overall rise in platelet counts irrespective of baseline platelet count.

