5.3 DATA ANALYSIS GENERAL CONSIDERATIONS

The FAS will be used as the primary population for all efficacy analyses, while the PP will be used in supportive analyses of the primary efficacy endpoint and Safety analysis set will be used for all safety analyses. Unless stated otherwise, all efficacy analyses will be performed at $\alpha=0.05$ significance level and only descriptive statistics or frequency count will be generated for safety analyses without any hypothesis testing.

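### The per-protocol timing rule (procedure on Day 8 to 15) makes no exception for the delay that the protocol permits when the Visit 4 platelet count exceeds 200 ×10⁹/L

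*SAP*

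**What the plan says.** Two of the PP exclusion criteria in SAP section 5.2.1 concern the timing of the procedure: "Did not have a protocol permitted procedure on Day 8 - 15" and "No elective procedures or elective procedure outside day 8-15". Neither carries an exception. SAP section 7 records the PP criteria as finalized.

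Protocol section 9.1 sets the scheduling window: "The elective procedure must be scheduled to be performed within 10 to 13 days of first dose of study drug". Protocol section 9.1.2.3 then provides that, when the Visit 4 count is above 200 ×10⁹/L, the procedure "may be delayed at the discretion of the investigator until platelet counts are below" that level. No latest day is given. The provision also appears in the protocol Synopsis, in protocol sections 7.2.1 and 9.1, and in SAP section 3.2.

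Protocol section 9.7.1.2 bases PP exclusion on major protocol violations, prohibited medication that affects the endpoints, and non-compliance with study drug. SAP section 5.3 makes the FAS the primary efficacy population, "while the PP will be used in supportive analyses of the primary efficacy endpoint".

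**The concern.** A PP analysis is meant to show what happens in subjects who adhered to the protocol. Here a subject can adhere fully and still be excluded, because the protocol allows the procedure to move and the PP rule does not.

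The trigger is also an outcome of treatment. Entry requires a mean count below 50 ×10⁹/L with neither count above 60, so a count above 200 about ten days later is hard to explain without active drug. An exclusion that depends on the response after randomization, and probably falls on one arm, weakens the comparability of the arms in the PP set. It would tend to remove avatrombopag subjects who did not need a transfusion. A gap between the PP and FAS results could then be read as an adherence effect when part of it comes from the exclusion rule.

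**Working it through.** **1. Is the permitted delay treated as a deviation anywhere?**

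- Protocol 9.7.1.2: a delay that the protocol permits is not a major violation, prohibited medication or non-compliance.
- SAP 8.1: for subjects with a procedure, the Visit 4 window runs to the actual procedure day and Visit 5 is counted from that day. The visit windows therefore accommodate a delay.
- SAP 5.1.1: the primary endpoint runs to 7 days after the procedure, so a delayed subject can be fully evaluated.

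Only the timing criteria in SAP 5.2.1 are out of line. The two also overlap: a subject with no procedure, or with one outside Day 8 to 15, already fails the criterion that asks for a permitted procedure in that window. An exception added to one criterion alone would be undone by the other.

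**2. How much room does the window leave?** Visit 4 falls on Day 10 to 13. Day 15 is 15 − 13 = 2 to 15 − 10 = 5 days later. Protocol 7.1.2.3 reports for the Phase 2 study that "the highest platelet count responses were observed between Days 10 to 14 after first dose". A delay past Day 15 is therefore possible. The documents do not say how often it would occur.

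**3. The plan's own power figure.** Inputs from SAP section 4: 67 avatrombopag and 33 placebo per cohort, 18% placebo response, a 35-point difference (so 53%), and Fisher's exact test at two-sided 0.05. Exact enumeration over both binomial distributions gives 92.6% power, which agrees with the stated figure of more than 90%.

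**4. How many subjects could be affected?** Protocol 9.4.4 aims to keep the share above 200 ×10⁹/L under 2%. At that ceiling:

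- per cohort: 67 × 0.02 = 1.34 avatrombopag subjects;
- overall: 133 × 0.02 = 2.66;
- chance of at least one such subject among 133, if subjects are independent: 1 − 0.98¹³³ = 93%.

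A count above 200 is thus likely to arise at the ceiling. Whether it leads to a delay past Day 15 is unknown.

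**5. Worst-case shift in the PP response.** Suppose a fraction x of the avatrombopag arm is removed and all of those removed were responders. The remaining rate is (0.53 − x)/(1 − x).

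| Share removed | PP response | Difference from 18% |
|---|---|---|
| 2% (protocol ceiling) | 0.51/0.98 = 52.0% | 34.0 points |
| 5% (assumption) | 0.48/0.95 = 50.5% | 32.5 points |
| 10% (assumption) | 0.43/0.90 = 47.8% | 29.8 points |

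In whole subjects, the planned number of responders is 67 × 0.53 = 35.51.

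| Responders removed | PP response | Power, Fisher's exact test |
|---|---|---|
| 1 | 34.51/66 = 52.3% | 92.2% |
| 2 | 33.51/65 = 51.6% | 90.0% |
| 3 | 32.51/64 = 50.8% | 89.0% |

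**6. Outer bound, not a forecast.** Protocol 7.2.1 says of the cited eltrombopag study that "26% of eltrombopag-treated subjects reached" a count above 200. If 26% applied here and every case were delayed past Day 15, 67 × 0.26 = 17.42 subjects would go and the rate would be (35.51 − 17.42)/49.58 = 36.5%. That is another drug, and the doses in this trial were chosen to avoid such counts.

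**The case against.** The strongest reply is that very little follows from the gap.

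- Removal needs three things together: a Visit 4 count above 200, an investigator who chooses to delay, and a procedure after Day 15. A reader might infer that strong responders as a group are removed. The documents do not support that. A strong responder at or below 200, one not delayed, or one delayed only to Day 14 or 15 stays in the PP set. The Day 8 to 15 window already adds two days on the late side of the scheduled window.
- The Day 10 to 14 peak comes from a Phase 2 study with a loading dose, which Phase 3 dropped (protocol 7.1). Protocol 7.2.1 expects elevations to be transient. No document gives the duration of counts above 200.
- That the affected subjects would be nearly all on avatrombopag is a reasonable inference, but no figure by arm is given for this trial.
- The subjects are not lost to evaluation. They stay in the FAS, where counts of at least 200 are tabulated by visit (SAP 5.4.3.2), and in the Safety Analysis Set if they meet its definition.
- A common procedure window is a defensible aim for a PP set, and SAP 5.2.1 justifies its exclusions by possible bias. An exemption tied to a count above 200 also depends on a post-randomization value, and subjects who are late for other reasons remain excluded.

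The first four points stand and set the size of the issue. The last stands in part. The exemption does favour one arm in practice, but it separates subjects who followed the protocol from those who did not, which is the purpose of a PP set. Reporting the number by arm makes its effect visible. None of these points supplies the missing exception.

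**Conclusion.** The inconsistency is real and minor. As written, SAP 5.2.1 can drop a protocol-compliant subject from PP because of a treatment-driven platelet rise.

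At the protocol's projection of under 2%, the loss is at most about 1.3 of 67 per dose group and 2 to 3 of 133 overall. The PP response would move by about one point, from 53% to about 52%. This assumes that every subject above 200 is delayed past Day 15 and is a responder; the actual number could be zero. The 5% and 10% rows are assumptions without support in the documents for this regimen.

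A reader might infer that the trial's conclusion is at risk. It is not. Success and gatekeeping rest on the FAS, PP is one of four listed sensitivity analyses, and removing avatrombopag responders biases PP against the drug.

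**What to change.** Before unblinding, reconcile SAP 5.2.1 with protocol 9.1.2.3:

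1. Merge the two timing criteria into one, for example: *No protocol-permitted elective procedure on Study Day 8 to 15. A procedure after Day 15 that was delayed under protocol section 9.1.2.3 for a Visit 4 platelet count above 200 ×10⁹/L is not an exclusion.* The outcome of such a subject is taken to 7 days after the actual procedure, as the endpoint already defines.
2. Report by treatment group the number of subjects whose procedure was delayed on this ground past Day 15. SAP 5.2.1 already summarizes set membership by group, but not by reason.

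The cost is one clause in the SAP and one line in a table. No new data are needed: the Visit 4 count is recorded, and SAP 8.1 already relies on the actual procedure day. The clinical rule on delaying the procedure is left as it is.
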